## 11 SELECTION OF STUDY POPULATION

### 11.1 Population Base

Any opioid-dependent subject about to undergo complete or partial opioid withdrawal and could benefit for a minimum of a 7-day treatment with lofexidine will be eligible for the study. Entry into this study is open to both men and women and to all racial and ethnic subgroups. An attempt will be made to include at least 25% female subjects, a mix of ethnicities reflecting the distribution in the local geographic regions of the study sites, and a minimum of 50 subjects each on methadone or buprenorphine maintenance treatment. Subjects will be recruited from a variety of sources, including subjects seeking treatment for opioid dependence via referrals from local treatment providers, word of mouth among subjects themselves also seeking treatment, and advertising in the local media. Recruitment advertisements will be approved by each site's Institutional Review Board (IRB).

Potential subjects may be accepted for screening after the nature and purpose of the investigation have been explained to them and after they have voluntarily given written informed consent (see Section 16.4).

### 11.2 Study Entrance Requirements

#### 11.2.1 Inclusion Criteria

To be eligible for participation, subjects must meet all of the following criteria:

1. Be able to verbalize understanding of the consent form, able to provide written informed consent, and verbalize willingness to complete study procedures.
2. Be male or female at least 18 years of age.

3. Have current dependence, according to the Mini International Neuropsychiatric Interview (M.I.N.I.) [18, 19], on any opioid (including methadone and buprenorphine maintenance treatment).
4. Be seeking treatment for partial or total withdrawal from current opioid and expected, as determined by the Principal Investigator, to benefit from lofexidine treatment for at least 7 days at clinically relevant doses (3.2 or 2.4 mg/day). This can include a variety of clinical situations where opioid withdrawal illness is likely to occur. Examples include:
  - abrupt and total withdrawal (including from methadone and buprenorphine);
  - agonist-assisted total withdrawal;
  - dose reduction of maintenance treatment (e.g., methadone, buprenorphine); and
  - transition from an opioid agonist to naltrexone or buprenorphine maintenance.
5. Urine toxicology screen positive for opioid(s) relevant to the subject's withdrawal treatment goal (can include methadone and buprenorphine) at Screening.
6. If female and of childbearing potential, subject must agree to use of one of the following methods of birth control:
  - oral contraceptives;
  - patch;
  - barrier (diaphragm, sponge or condom) plus spermicidal preparations;
  - intrauterine contraceptive system;
  - levonorgestrel implant;
  - medroxyprogesterone acetate contraceptive injection;
  - complete abstinence from sexual intercourse;
  - hormonal vaginal contraceptive ring; or
  - surgical sterilization or partner sterile (must have had documented proof).

### 11.2.2 Exclusion Criteria

Subjects who meet any of the following criteria will not be allowed to participate:

1. Be a female subject who is pregnant or lactating.
2. Have a very serious medical illness not under control as detailed below.
  - Serious medical illness will be determined at Screening by:
    - medical history;
    - physical examination;
    - 12-lead electrocardiogram (duplicate);

- clinical laboratory tests, including standard lab tests, an infectious disease panel for syphilis (subject is excluded if positive for active syphilis as per required laboratory tests; see also Section 15.5.4.2) and hepatitis (positive results do not exclude a prospective subject from participation unless there is an indication of active liver disease); and
- tuberculin test (purified protein derivative [PPD]) and/or a chest x-ray (a positive PPD result does not exclude a prospective subject from participation, but if diagnostic tests [e.g., chest x-ray] indicate that active disease is present, the subject will be excluded from participation; see also Section 15.5.4.2).
- Have active self-reported acquired immune deficiency syndrome (AIDS) or self-reported human immunodeficiency virus (HIV) positive status and taking retroviral medications currently or within the past 4 weeks.
- Have an unstable psychiatric condition (e.g., suicide risk, per Investigator judgment).

3. Current dependence (based on the M.I.N.I.) on any psychoactive substance (excluding caffeine, nicotine, and the subject's current opioid-dependence agent, which can include methadone and buprenorphine, for example, in agonist-maintained subjects) that requires detoxification or dose reduction as part of the pre-defined individual subject withdrawal treatment goal.
4. Have participated in an investigational drug study within the past 30 days.
5. Have history of lofexidine exposure in a prior clinical trial or otherwise.
6. Abnormal cardiovascular exam at screening, including any of the following:
  - clinically significant abnormal electrocardiogram (ECG) (e.g., second or third degree heart block, uncontrolled arrhythmia, or QTcF intervals greater than 450 msec for males and greater than 470 msec for females);
  - resting pulse less than 55 bpm or symptomatic bradycardia;
  - resting systolic blood pressure less than 95 mmHg or symptomatic hypotension;
  - resting diastolic blood pressure less than 65 mmHg;
  - resting blood pressure greater than 155/95 mmHg; or
  - prior history of myocardial infarction.

Note: if a QTcF interval, blood pressure, or pulse value meets the above criteria, the value should be confirmed by repeating the measurement (twice, if necessary). If 2 of 3 values meet the above criteria, the subject will be excluded from participation.

7. To avoid drug-drug interactions, subjects requiring the following will be excluded:
  - tricyclic antidepressants, which may reduce the efficacy of imidazoline derivatives; and
  - beta-receptor blockers, to avoid the risk of excessive bradycardia.

[figure not shown]
### 11.3 Screening Failures

Screening failures are potential study subjects who provide informed consent and fail inclusion and/or exclusion criteria or for other reasons are not allowed to participate. A screening log for all subjects who are screened will be maintained. The screening log will uniquely identify each subject and report whether he or she passed or failed screening, and, if he or she did not pass, the reasons for the screening failure.

## 12 INVESTIGATIONAL AGENTS

### 12.1 Lofexidine Hydrochloride

Lofexidine hydrochloride is an  $\alpha_2$ -adrenergic agonist with mild to moderate antihypertensive actions. It has the empirical formula  $C_{11}H_{13}C_{13}N_2O$  representing a molecular weight of 295.61. The structural formula is:

Lofexidine hydrochloride is a synthetic product and has the chemical designation of 2-[1-(2,6-dichlorophenoxy)ethyl]-4,5 dihydro-1*H*- imidazole monohydrochloride. It is a white to off-white crystalline powder that is very soluble in water and ethanol. It is lightly soluble in 2-propanol and practically insoluble in ether. Lofexidine hydrochloride melts at approximately 126-128°C.

Lofexidine will be supplied by the Sponsor (USWM) in peach colored tablets containing 0.2 mg of active medication for oral administration.

### 12.2 Dispensing Investigational Agent

Lofexidine will be packaged and distributed through the pharmacy coordinating center (Sharp). Lofexidine tablets will be supplied in uniquely-identified 80-count bottles. During in-clinic treatment, lofexidine doses will be dispensed directly from the 80-count bottles, whereas for outpatient treatment doses will be dispensed by the study pharmacist as determined clinically appropriate by the Principal Investigator or designee to the subject in individual prescription bottles. One to 2 days of medication may be dispensed at each daily clinic visit to accommodate flexible scheduling (e.g., day and a half worth of medication to supply subject from one morning to the next afternoon depending on availability for clinic visit). The site will maintain a dispensing log for each bottle and document the number of tablets dispensed to each subject along with the number of tablets returned, if any, by the subject at each outpatient visit. Returned tablets will not be re-dispensed to future subjects.

All study medication will be dispensed by the site pharmacist or designee.

### **12.3 Blinding Plan**

This is an open-label study.

### **12.4 Labeling**

The investigational agent, lofexidine, will be packaged in labeled bottles (80 count pills) and during the outpatient portion of the study dispensed to subjects in labeled prescription bottles (i.e., redispensing container). The product label will include the sponsor's name, protocol number, the number of tablets in the bottle, address, 24-hour emergency phone number, and the following statement – “Caution: New Drug – Limited by Federal Law to Investigational Use.”

During outpatient treatment (Days 4-14), sites may dispense 1 to 2 days of medication at each daily clinic visit to accommodate flexible scheduling for use in an outpatient setting (e.g., day and a half worth of medication to supply subject from one morning to the next afternoon depending on availability for clinic visit). In such cases, the redispensing container will include a subject label, supplied by the study site, and will include the following information:

- Principal Investigator's name and number,
- Subject number,
- Date of dispensing,
- Directions for use,
- Drug name / dose or protocol number,
- Number of pills dispensed,
- Sponsor's name, and
- For Investigational Use Only.

### **12.5 Storage**

The investigational agent, lofexidine, will be stored at 68-77°F in a secure location at the dispensing pharmacy or site. Temperature of the investigational agent will be maintained at 68-77°F during transport. Temperature of the investigational agent will be monitored during storage and transport. Temperature excursions will be reported to the Sponsor and the Sponsor will determine if the investigational agent is fit for use.

### **12.6 Record of Administration**

Accurate recording of all investigational agent received, dispensed, administered, and returned will be maintained by study site personnel. During outpatient treatment (Days 4-14), subjects are to record doses taken in his/her subject diary.

## **12.7 Used/Unused Supplies**

Unused investigational agent will be retained at the participating sites to enable a full investigational drug inventory by the sites' respective monitor. If any investigational agent is lost or damaged, its disposition should be documented. The Sponsor will provide instructions to return the unused study drug to the pharmacy coordinating center periodically throughout the study (following monitor review) or at the end of the study for proper destruction in accordance with local and federal regulations.

## **12.8 Contraindications**

Clonidine is specifically prohibited in this study.

To avoid drug-drug interactions, lofexidine should not be administered concurrently with:

- tricyclic antidepressants – may reduce the efficacy of imidazoline derivatives; and
- beta-receptor blockers – the combination of lofexidine and beta-receptor blockers should be used with caution to avoid the risk of excessive bradycardia.

Lofexidine may enhance the effects of antihypertensive drug therapy and appropriate caution is warranted in subjects on such therapy. The Principal Investigator may need to lower the subject's antihypertensive dose during the study.

Lofexidine should generally not be administered concurrently with alcohol, sedatives, and anesthetics as these may interact with lofexidine and enhance its central sedative effects.

# **13 TREATMENT PLAN**

## **13.1 Investigational Agent**

All subjects in this study will receive lofexidine, as described in Section [13.2](#).

## **13.2 Dose Administration**

### **13.2.1 Administration of Doses**

Lofexidine administration should be initiated in concurrence with the change in opioid dose which is anticipated to elicit withdrawal symptoms (e.g., first day of dose reduction, or first day of abrupt cessation) or on the first day of emergence/anticipated emergence of such symptoms as determined at the Investigator's discretion. Details regarding the timing of lofexidine therapy initiation relative to change in opioid dose and onset/expected onset of symptoms should be captured in the source. All subjects will take lofexidine orally for 7 days, starting on Day 1 at a dose of 3.2 mg per day (0.8 mg QID), with lowering of the dose allowed to 2.4 mg daily (0.6 mg QID) if required for tolerability based on the subject's individual treatment goal and response per clinical judgment of the Principal Investigator. The subject's dose may be changed back to 3.2 mg/day, per Principal Investigator judgment, but in no case is the dose of lofexidine to exceed 3.2 mg/day (or a single dose of 0.8 mg). Supporting rationale for any dose changes must be recorded in the subject's source document.

All subjects will receive all 4 doses of lofexidine in a clinic setting for the first 3 days (Days 1-3) and then, per clinical judgment of the Principal Investigator, subjects can continue to receive lofexidine doses in a clinic setting or can be treated outside of the clinic (outpatient) for the remaining 4 days of mandatory lofexidine treatment (Days 4-7). Note that the decision to allow outpatient treatment should take into account the subject's sensitivity to the hypotensive effects of the study medication (as observed over Days 1-3) and the subject's potential for noncompliance. Furthermore, the rationale for the decision to continue treatment through either an in-clinic or outpatient setting must be documented in the subject's source document.

During in-clinic treatment, subjects must take lofexidine within a 1-hour window, 30 minutes before or after 8 AM and within a 30-minute window, 15 minutes before or after 1 PM, 6 PM, and 11 PM, with the actual date and time of each dose recorded in the subject's source document and in the eCRF. For subjects receiving outpatient treatment (elective) on Days 4-7 and those continuing optional lofexidine treatment in an outpatient setting for up to an additional 7 days (Days 8-14), prescribed dosing will remain on the same QID schedule (8 AM, 1 PM, 6 PM, 11 PM) with compliance assessed at the next day's clinic visit by pill count, subject report of dosing in diary ([Appendix 3](#)), and a fingerprick blood sample to assess plasma lofexidine concentrations. Note that if the subject is receiving outpatient treatment, he/she is required to take a dose of lofexidine in the clinic at each daily clinic visit.

#### Optional Outpatient Treatment (Days 8-14)

Per Principal Investigator judgment, subjects can continue lofexidine treatment on an outpatient basis for up to an additional 7 days, per the dose schedule listed below, including taking a dose of lofexidine in the clinic at each daily clinic visit. The rationale for the decision to continue lofexidine treatment must be documented in the subject's source document. Note that lofexidine dosing may be stopped at any time during Days 8-14. No subject will receive lofexidine for more than 14 days total in this study.

Day	If Dose Regimen on Day 7 is 3.2 mg/day (0.8 mg QID)	If Dose Regimen on Day 7 is 2.4 mg/day (0.6 mg QID)
8	2.4 mg/day (0.6 mg QID)	1.6 mg/day (0.4 mg QID)
9	2.4 mg/day (0.6 mg QID)	1.6 mg/day (0.4 mg QID)
10	2.4 mg/day (0.6 mg QID)	1.6 mg/day (0.4 mg QID)
11	1.6 mg/day (0.4 mg QID)	0.8 mg/day (0.2 mg QID)
12	1.6 mg/day (0.4 mg QID)	0.8 mg/day (0.2 mg QID)
13	0.8 mg/day (0.2 mg QID)	0.8 mg/day (0.2 mg QID)
14	0.8 mg/day (0.2 mg QID)	0.8 mg/day (0.2 mg QID)

Note: In order to prevent dehydration from opioid withdrawal, increased fluid intake will be encouraged from the beginning of the study.

### 13.2.2 Dose Hold Criteria

Study medication will be held if pre-dose vital signs meet any of the criteria listed below (see Section 10.4 for details on repeat confirmatory requirements).

#### Resting (sitting [or recumbent if necessary because of an AE])

- Systolic blood pressure <90 mmHg and >20% below screen value;
- Diastolic blood pressure <50 mmHg and >20% below screen value;
- Pulse <50 bpm and >20% below screen value; or
- Symptoms of hypotension and/or bradycardia (e.g., lightheadedness, dizziness).

#### Orthostatic (after standing for 3 minutes)

- Systolic blood pressure diastolic blood pressure, or pulse >25% below recumbent values.

During outpatient treatment, if the subject experiences symptoms of hypotension and/or bradycardia (see below), he/she should call the study site and the site should instruct the subject on whether the next dose should be delayed, skipped, or he/she should be seen in the clinic. The subject should record this information in the subject diary (Appendix 3).

- marked dizziness
- fainting (especially when standing from a sitting or lying position)
- light headedness
- Fatigue
- Weakness
- shortness of breath
- chest pains
- easily tiring during physical activity
- confusion or memory problems
- blurred vision
- nausea
- cold, clammy pale skin
- rapid shallow breathing
- depression
- thirst

All instances of dose-holds must be clearly documented in the subject's source document and dosing eCRF, and the event causing the dose hold should be recorded on the AE or SAE eCRF, as applicable.

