## **10.4 Dose Hold and Discontinuation Criteria (2 of 3 Rule)**

When a blood pressure, heart rate, or QTcF interval value meets criteria for withholding a dose (Section 13.2.2) or discontinuation from the study (Section 13.2.3), the value needs to be confirmed by the site personnel by repeating the vital sign measurement or ECG recording, approximately 10 to 15 minutes later. If the value is confirmed by the second measurement, the appropriate action will be taken (dose hold or study discontinuation) and the confirmatory value will be recorded in the subject's source document and appropriate eCRF. If the second value does not meet the specified criteria, a third measurement will be taken approximately 10 to 15 minutes later. If this value is confirmatory, the appropriate action will be taken (dose hold or study discontinuation) and the last confirmatory value will be recorded in the subject's source document and appropriate eCRF. If the third value does not confirm the initial finding, then no action should be taken and the third value should be entered in the subject's source and appropriate eCRF. Note that should a second or third measurement be required with waiting between measurements, the timing of the

measurement will not be considered a protocol deviation (i.e., outside the protocol-specified window).

Whenever blood pressure, heart rate, or QTcF interval values meet dose hold or study discontinuation criteria, these are to be recorded on the subject's eCRF as an adverse event (AE) or serious adverse event (SAE), as applicable. Examples are:

Item	Record Adverse Event of:
Resting Vital Signs	
SBP <90 mmHg and >20% below screen value	Hypotension
DBP <50 mmHg and >20% below screen value	Hypotension
Pulse <50 bpm and >20% below screen value	Bradycardia
Orthostatic Vital Signs	
SBP >25% below recumbent values	Postural hypotension
DBP <25% below recumbent values	Postural hypotension
Pulse >25% below recumbent values	Postural bradycardia

DBP = diastolic blood pressure, SBP = systolic blood pressure

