- (a) The Baseline period is the morning of admission, before dosing.
- (b) This form is to be updated at Baseline.
- (c) A chest x-ray is required only if a PPD skin test for tuberculosis is not done, the current PPD is positive, or if a past PPD was positive.
- (d) The urine sample collected on the first day of screening will be divided into two aliquots. One sample will be sent to the central lab for urinalysis and the other sample will be used for urine drug screening and immediate "dipstick" analysis of pregnancy (females only).
- (e) A complete physical exam will be done on Day 1 (3-4 hours after first dose) and as clinically warranted.
- (f) Subjects may be admitted to the hospital or clinic in the evening (Day -1) before study drug administration on Day 1.
- (g) Per Investigator judgment, subjects can be discharged from the study after receipt of at least one dose of study drug on Day 7 and after completion of all end-of-study procedures.
- (h) Baseline 12-lead electrocardiograms (ECGs) will be done on one day during the screening period at 8 AM (or as close to 8 AM as possible) and at 11:30 AM. Note that a time delay for the 8 AM ECG will not be considered a protocol deviation, but that the second ECG should be taken 3.5 hours after the first ECG.
- (i) 12-lead ECGs (duplicate) before dosing on Day 1 at 8 AM and 3.5 hours ( $\pm$  15 minutes) after dosing.
- (j) 12-lead ECGs (duplicate) before subject's last dose and 3.5 hours after dosing (or as close to this time as possible) or, if applicable, at discontinuation from the study.
- (k) Urine drug screen will be done every day in an in-clinic setting to monitor for contraband and every day in an outpatient setting to monitor illicit drug use.
- (l) During in-clinic treatment, resting (sitting [or recumbent if necessary because of an adverse event]) and standing (if able) blood pressure and pulse will be measured before every dose and 3.5 hours after study medication administration at 8 AM, 1 PM, and 6 PM; respiration and temperature before 8 AM dose only.
- (m) During outpatient treatment, resting (sitting [or recumbent if necessary because of an adverse event]) and standing (if able) blood pressure and pulse will be measured before an in-clinic dose of lofexidine each day and 3.5 hours after dosing on Days 4-13 and once before any dose on Day 14 and at the End of Treatment/Study Discontinuation visit. Oral temperature and respiration are not required measurements during outpatient treatment.

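### The diastolic row of the Section 10.4 orthostatic table is reversed, and the orthostatic rule names recumbent values although the paired resting reading is scheduled sitting

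*Protocol*

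**What the plan says.** **The hold rule.** Protocol 13.2.2 opens with "Study medication will be held if pre-dose vital signs meet any of the criteria listed below". Its orthostatic bullet, applied after three minutes of standing, is "Systolic blood pressure diastolic blood pressure, or pulse >25% below recumbent values". The dose-hold list under Vital Signs Measurements in SAP 6.9 carries the same bullet with the same direction.

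**The AE table.** Protocol 10.4 requires values that meet the hold or discontinuation criteria to be entered as AEs, and then gives a table of examples with the term to use. The systolic row is "SBP >25% below recumbent values", and the pulse row runs in the same direction. The diastolic row is "DBP <25% below recumbent values". The terms assigned are postural hypotension (both pressure rows) and postural bradycardia (pulse).

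**The posture of the resting reading.** Notes (l) and (m) to Table 1 schedule "resting (sitting [or recumbent if necessary because of an adverse event]) and standing (if able) blood pressure and pulse". Sections 15.3.1 to 15.3.3 and 15.5.2 say the same. The orthostatic procedure in 15.5.2 is three minutes at rest, a reading, three minutes standing, and a second reading. It contains no lying-down step. Screening vital signs are sitting and standing.

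**The concern.** Two slips sit in the same rule.

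- **Direction.** The diastolic row of 10.4 contradicts the rows above and below it and contradicts 13.2.2, which covers diastolic pressure explicitly. Sites consult this table to choose an AE term.
- **Reference.** The resting heading in 13.2.2 itself separates sitting from recumbent and reserves recumbent for subjects with an AE. The orthostatic bullet that follows then measures the fall from recumbent values. No sentence says that the sitting reading stands in for it.

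Safety is the primary objective, and 17.3 names orthostatic hypotension and orthostatic bradycardia as AEs of special interest. The criterion drives dose holds on pre-dose readings and, through 10.4 and 15.5.2, AE entries on pre-dose and post-dose readings. The AE summaries are built from what sites enter, so a contradictory instruction to about 20 sites deserves correction even if most would see through it.

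**Working it through.** The plan states no figure to reproduce here. The check is a comparison of texts plus threshold arithmetic.

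**A. The diastolic row**

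Inputs: the 25% threshold (10.4, 13.2.2, SAP 6.9), and the lowest and highest resting diastolic pressures that pass screening. Section 11.2.2 excludes "resting diastolic blood pressure less than 65 mmHg" and "resting blood pressure greater than 155/95 mmHg", so the limits are 65 and 95 mmHg. I add 80 mmHg as an assumed middle value. On-treatment resting values may lie outside this range; the limits serve only to illustrate.

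Fall = (resting − standing) / resting. The cutoff is 0.75 × resting. Readings are taken as whole mmHg, and the row as written is taken to mean a fall above zero and under 25%.

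| Resting | Cutoff | Meets 13.2.2 (over 25%) | Meets 10.4 row as written (under 25%) | Check |
|---|---|---|---|---|
| 65 | 0.75 × 65 = 48.75 | 48 or below | 49 to 64 | 49: 16/65 = 24.6%; 48: 17/65 = 26.2% |
| 80 (assumed) | 0.75 × 80 = 60 | 59 or below | 61 to 79 | 70: 10/80 = 12.5%; 55: 25/80 = 31.25% |
| 95 | 0.75 × 95 = 71.25 | 71 or below | 72 to 94 | 72: 23/95 = 24.2%; 71: 24/95 = 25.3% |

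The two readings are mutually exclusive: no fall that meets one meets the other. The Amendment 01 copy of the protocol carries the same row, so a fault in reading the PDF is unlikely.

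**B. The reference posture**

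The recumbent reference appears in five places in the current text: three rows in 10.4, one bullet in 13.2.2 and one bullet in SAP 6.9 (3 + 1 + 1 = 5). Against these:

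- Table 1 notes (l) and (m), 15.3.1 to 15.3.3 and 15.5.2: resting means sitting, with recumbent only when an AE requires it.
- SAP 6.9: the vital-sign summaries are for sitting and standing readings only.

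At an ordinary time point, therefore, one resting value exists and it is a sitting one.

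The documents do not say how sitting and recumbent pressures differ. As an assumed example, a recumbent systolic pressure of 120 gives a cutoff of 0.75 × 120 = 90 mmHg. Sitting values from 115 to 130 would give 0.75 × 115 = 86.25 to 0.75 × 130 = 97.5 mmHg. The choice of reference can matter, but only where more than one is available or where a programmer insists on the named one.

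**The case against.** The strongest reply is that neither slip changes what a sensible reader would do.

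**On direction.** Under 10.4 an AE is entered when a value meets the hold or discontinuation criteria, and 15.5.2 likewise points to 13.2.2 and 13.2.3. The table only illustrates. Under the governing rule, with the paired resting value as reference, a standing 48 from a resting 65 is recorded and a standing 60 is not. A row that calls a 1% fall postural hypotension is a visible misprint between two correct rows, and SAP 6.9 has the right sign. This stands. A reader might infer that large diastolic falls would go unrecorded across the trial; the documents do not support that, because 13.2.2 is the trigger.

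**On posture.** The Table 1 row and 15.2 group sitting and recumbent together as the resting position, 15.5.2 yields one resting value for each standing value, and SAP 6.9 pairs resting with standing when it counts missed standing readings. This also largely stands. A reader might infer that the rule has no usable reference, or that it catches only subjects laid down for an AE. That is too strong: a paired resting value is scheduled at each time point, and only its label is wrong.

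**On the analysis.** SAP Table 2 defines the events of special interest by AE terms and not by the 25% threshold, and holds are recorded on the dosing form, so the dose-hold count need not be rebuilt from readings. Subjects with symptoms are caught by separate provisions in 13.2.2 and 15.5.2.

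What survives is that the written rule still contradicts itself on direction and names a posture that the schedule reserves for AEs. The two-of-three confirmation in 10.4 does not help, since it repeats a measurement without saying which direction or reference applies.

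**Conclusion.** Wrong as written on both counts; low severity.

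The diastolic row of 10.4 is reversed against its own table, 13.2.2 and SAP 6.9. Its practical reach is the choice of AE term at a site that follows the example in place of the rule.

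The posture label is a misnamed reference. On the assumption that sites use the paired sitting value, which 15.5.2 makes likely, the remaining exposure is twofold. First, asymptomatic orthostatic falls may be handled inconsistently. Second, SAP 6.9 plans a table of dose-reduced subjects who still meet the criteria after the reduction. If that table is derived from readings using the stated wording, the named comparator exists only where a recumbent reading was taken because of an AE. The SAP does not say how the table is to be derived.

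The number of subjects or readings affected cannot be estimated from the documents.

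**What to change.** 1. In the 10.4 table, change the diastolic row from less than 25% to more than 25%.
2. In all five places (three rows in 10.4, one bullet in 13.2.2, one in SAP 6.9), replace the reference to recumbent values with: *the paired resting value (sitting or, if applicable, recumbent) taken immediately before standing*. Keep the 25% threshold.

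Make both edits together, because correcting the posture alone leaves the diastolic row reversed. An optional sentence in SAP 6.9 could say how recumbent readings taken because of an AE enter the sitting summaries.

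The cost is one sign and one phrase in five places. No threshold, visit or measurement changes.
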